11.2.6 Response analysis

All tumour response measurements (pre- and post-treatment) must be recorded using the definitions of RECIST 1.1 following SABR treatment. RECIST assessments will take into account post-treatment inflammatory processes that occur after SABR treatment in pulmonary and liver tissues.

DCR, ORR at 3, 6, 12 and 24 months and best overall response will be described as percentages with exact 95% confidence intervals for: a) DCR; b) ORR at 3, 6, 12 and 24 months and c) best overall response. If at least one patient has non-target disease only with response classified as non-CR/non-PD, then the response rate of CR will be reported instead of CR+PR.

The change in lesions size over time will be displayed graphically on the subset of lesions with measurable disease at baseline, with each lesion represented as a separate line and line colour representing the radiotherapy modality (SABR or conventional RT).

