6.3 Secondary Objectives

Secondary objectives are to examine evidence of clinical efficacy of the combination:

1. To describe overall survival (OS).
2. To describe time to local progression (TTLP).
3. To describe distant progression free survival (DPFS).
4. To describe overall response rate (ORR).
5. To describe disease control rate (DCR)
6. To describe changes in pain ratings over time.

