7.14 Rationale of Endpoints Definition

Primary Endpoint:

Safety (acute and long term) will be evaluated using CTCAE version 4.03 in all patients who have received at least one SABR treatment and one dose of pembrolizumab. Acute adverse events (AE) are defined as AEs occurring from the time of first SABR treatment to 30 days post

end of pembrolizumab treatment and long term AE are defined as AEs occurring after 30 days post end of pembrolizumab treatment.

Secondary Endpoints:

To evaluate effectiveness of the treatment combination, using the following measures:

- a) Overall survival (OS), time to local progression (TTLP), distant progression free survival (DPFS) and overall response rates
 - i. OS will be measured from the date of commencement of SABR treatment to the date of death from any cause.
 - ii. TTLP will be measured from date of commencement of SABR treatment to the date of first local progression. Death and commencement of a further course of systemic therapy will be considered as censoring events.
 - iii. DPFS will be measured from the date of commencement of SABR treatment to the date of first distant progression at site not documented at registration, or date of death from any cause for patients without distant progression. Commencement of second course of a further course of systemic therapy will be considered as censoring event.
- b) Overall response is defined as complete response or partial response, measured using RECIST 1.1 criteria. The RECIST definition of complete response has been modified to include disappearance of the target tumor radiographically or complete metabolic response. The primary is excluded from the evaluation of the overall response.
- c) Disease control is defined as complete response or partial response at any time after treatment commencement or stable disease for at least 6 months, measured using RECIST 1.1 criteria. The RECIST definition of complete response has been modified to include disappearance of the target tumor radiographically or complete metabolic response. The primary is excluded from the evaluation of the disease control.
- d) Pain will be evaluated using the Numerical Pain Rating Scale at the following time points: pre-conventional radiotherapy treatment (if CRT performed), pre-SABR treatment, prior to each cycle of pembrolizumab, then 3 monthly until 24 months after the end of SABR treatment.

Exploratory Endpoints

A number of translational endpoints will be evaluated including:

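### One non-target-only patient rated non-CR/non-PD replaces the defined response rate (CR+PR) with the CR rate for everyone analysed

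*Combined protocol and SAP*

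**What the plan says.** Section 6.3 lists describing the overall response rate as the fourth secondary objective. Section 7.14(b) defines the endpoint: "Overall response is defined as complete response or partial response, measured using RECIST 1.1 criteria". It makes two qualifications. CR is widened to include complete metabolic response, and "The primary is excluded from the evaluation of the overall response". Neither concerns patients who have only non-target disease.

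Section 11.2.6 plans exact 95% intervals for DCR, for "b) ORR at 3, 6, 12 and 24 months and c) best overall response". It then adds: "If at least one patient has non-target disease only with response classified as non-CR/non-PD, then the response rate of CR will be reported". The clause in full reads "then the response rate of CR will be reported instead of CR+PR".

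Three other places bear on the point:

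- Section 8.3, criterion 3, requires measurable disease by RECIST 1.1.
- Section 11.2.1 counts as response-evaluable at a visit those treated participants who were scanned at that visit.
- Section 11.1 says the results are meant to be descriptive.

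**The concern.** The trigger is one patient, but what it replaces is a rate. The natural reading is that the summary changes for all patients analysed, although the text does not say so in those words. Because the CR rate stands in place of CR+PR, the endpoint defined in section 7.14 would have no row in the response table, and no other section restores it.

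The scope is also unstated. The sentence does not say whether the switch applies only at the visit where the trigger occurs, at all four visits, or also to best overall response. It follows a list that includes DCR, which itself counts PR: "Disease control is defined as complete response or partial response at any time after treatment commencement".

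At stake are the meaning and comparability of the reported ORR. Which quantity is published would depend on the observed rating of a single patient, and a later reader comparing this cohort with another might have only a CR rate at the planned visits.

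**Working it through.** **Figures in the plan.** The documents give no expected CR, PR or overall response rate and no sample size for response, so there is no response figure to reproduce. As a check on the interval method, all 12 rows of Table 8 in section 11.2.9 reproduce with Clopper-Pearson limits at n = 30 (for example 3/30: 2-27%; 12/30: 23-59%). The same method is used below.

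**Can the trigger occur?** Criterion 3 makes it uncommon. It remains possible by inference:

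- Criterion 3 does not say that the measurable lesion must be a metastasis.
- Section 7.14 excludes the primary from response evaluation.
- Footnote 14 to Table 1 asks for a primary-surgery block only if the patient had that surgery, so an unresected primary is allowed for.
- Section 11.2.6 expects some lesions not to be measurable, since lesion size is to be "displayed graphically on the subset of lesions with measurable disease at baseline".

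A patient whose only measurable lesion is the primary, and whose metastases are all non-measurable, would have non-target disease only for response purposes. The documents give no frequency. If each of 30 patients independently had an assumed probability q of triggering the rule, the chance of at least one trigger is 1 - (1 - q)^30. That is 26% for q = 1%, 45% for q = 2% and 79% for q = 5%.

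**How far can triggering patients distort CR+PR?** Let n be the patients analysed, k the triggering patients (all non-responders) and r the responders (CR+PR).

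- Recoding all k as responders moves the rate by k/n.
- Excluding them moves it by r/(n - k) - r/n = rk/[n(n - k)]. This is at most k/n because r ≤ n - k.

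At n = 30 the bound is 1/30 = 3.3, 2/30 = 6.7 and 3/30 = 10.0 percentage points for k = 1, 2 and 3.

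**How far does the switch move the reported figure?** (CR + PR)/n - CR/n = PR/n. This exceeds k/n whenever PR > k, whatever n and the number of CRs. It therefore also holds for smaller by-visit denominators.

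**Illustration** (n = 30, 3 CRs, exact 95% CI; all counts assumed):

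| PRs | CR+PR as in 7.14 | After the switch (CR only) | Change, points |
|---|---|---|---|
| 1 | 4/30 = 13.3% (3.8-30.7) | 3/30 = 10.0% (2.1-26.5) | 3.3 |
| 3 | 6/30 = 20.0% (7.7-38.6) | 10.0% (2.1-26.5) | 10.0 |
| 6 | 9/30 = 30.0% (14.7-49.4) | 10.0% (2.1-26.5) | 20.0 |
| 12 | 15/30 = 50.0% (31.3-68.7) | 10.0% (2.1-26.5) | 40.0 |

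With 1 PR and k = 1 the two effects are equal. The table compares two different quantities. It shows how much goes unreported and does not show bias in either rate.

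**The case against.** The strongest reply is that eligibility nearly closes the trigger. Every correctly enrolled patient has measurable disease, no passage describes a patient whose only measurable lesion is the primary, and the planned lesion-size plot is a lesion-level statement that fits patients with a mix of measurable and non-measurable metastases. This stands as a limit on likelihood. The plot alone does not show that a triggering patient will exist; it only makes the combination possible once the primary is set aside. If the sponsor believes the case cannot arise, the sentence serves no purpose and can be deleted.

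A second reply is that the rule is prespecified, can only lower the reported rate for a given set of ratings, and has a reason: a patient with only non-target disease cannot be rated PR, so CR is the one response category open to everyone. That is a fair reason to show a CR rate. It is not a reason to drop the PRs of patients who do have measurable lesions, and showing both rates avoids the choice.

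A third is that little is lost. PRs still count in DCR as section 7.14 defines it, and CR+PR could be summed from best overall response if that is tabulated by category. Both points hold, but neither recovers CR+PR at 3, 6, 12 and 24 months, and the plan does not promise a category table.

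Finally, the size of the effect rests on assumed counts, and denominators at later visits may be below 30, so the illustrated intervals would not carry over to those visits. That is accepted. The comparison PR/n against k/n does not depend on those choices.

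**Conclusion.** The concern holds and is minor. Section 11.2.6 departs from the definition in section 7.14 without saying so there. If the trigger fires, the defined ORR is not reported at the planned visits. The reported figure drops by PR/n, which is larger than any distortion the triggering patients could cause (at most k/n) whenever PRs outnumber them. The conclusion assumes the natural reading that the switch applies to all patients analysed. How often it would apply is unknown. ORR is a descriptive secondary endpoint, so no error rate, power or stopping decision is affected.

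**What to change.** In section 11.2.6, change *instead of* to *in addition to*, so that CR+PR as defined in section 7.14 is always reported at each of the four visits and for best overall response, with the CR rate as an extra row. State that patients with non-target disease only count as responders only if rated CR, and give their number. Add one sensitivity row: CR+PR among patients with at least one measurable non-primary lesion at baseline.

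The drawback is that CR+PR in all patients is slightly conservative, because non-target-only patients cannot score PR. With 1, 2 or 3 such non-responders the sensitivity row would be higher by:

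- 1.7, 3.6 or 5.6 points from an assumed 15/30 (15/29 = 51.7%, 15/28 = 53.6%, 15/27 = 55.6%, against 50.0%);
- 0.7, 1.4 or 2.2 points from an assumed 6/30 (6/29 = 20.7%, 6/28 = 21.4%, 6/27 = 22.2%, against 20.0%).

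If the switch is kept, put the exception into section 7.14 and say whether it applies per visit or throughout, and whether it reaches best overall response and DCR.

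The cost is a short edit to section 11.2.6 and one or two table rows, with no new data.

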11.2.7 Exploratory Endpoints

All exploratory endpoints (PD-L1 expression, TILs, peripheral blood markers and other markers) will be described over time using linear mixed models. The linear mixed model will include time as fixed effect (as factor) and patients as random effect. Mean and 95% confidence intervals will be calculated for each time point and the data will be displayed graphically. Contrasts from the LMM will be used to test whether there is a change in expression levels from baseline to post-treatment sample time points, baseline to cycle 8 and baseline to 12 months post SABR. Variable transformation may be required for some of the collected variables. If the assumptions of the model do not hold, simple descriptive statistics will be provided for each variable at each time point.

A number of further exploratory translational endpoints will be evaluated including

1. Primary and metastatic lesions for PD-L1 expression using immunohistochemistry. Protein expression of PD-L1 will be measured using a previous defined immunohistochemistry method on H&E stained slides using Merck's diagnostic PD-L1 assay. Changes in PD-L1 in primary and metastatic lesions (if accessible) will be evaluated. Levels of PD-L1 in Primary sample will be correlated with changes in levels of T cell activation and T cell immunosuppression from baseline to cycle 8 of pembrolizumab using spearman's correlation.
2. Primary and metastatic lesions for quantity of tumour infiltrating lymphocytes (TILs) using a previously defined method. TILs will be measured as a continuous variable using a previous defined method on H&E stained slides using percentage (%) infiltrating stromal located lymphocytic infiltration. Changes in TILs in primary and metastatic lesions (if accessible) will be evaluated. Levels of TILs in Primary sample will be correlated with changes in levels of T cell activation and T cell immunosuppression from baseline to cycle 8 of pembrolizumab using spearman's correlation.
3. Other immune endpoints including antibody titres and peripheral blood markers of immune activation and suppression
4. Seroconversion to a range of epitopes will be measured in serum samples. An assay to detect soluble PD-L1 assay will also be used.

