7.10.1 Immunity and Control of Renal Cancer Metastases

The importance of intact immune surveillance in controlling outgrowth of neoplastic transformation has been known for decades. Accumulating evidence shows a correlation between tumour-infiltrating lymphocytes (TILs) in cancer tissue and favorable prognosis in various malignancies. In particular, the presence of CD8+ T-cells and the ratio of CD8+ effector T-cells / FoxP3+ regulatory T-cells seems to correlate with improved prognosis and long-term survival in many solid tumours.

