11 STATISTICAL ANALYSIS PLAN

11.1 Statistical Analysis Plan Summary

This is a prospective, single arm Phase 1b/II study to evaluate the safety profile, efficacy and biological effects of SABR in combination with pembrolizumab in patients with oligometastatic renal cancer.

As the sample size of 30 in this study is a pragmatic one, to demonstrate a safety and efficacy signal, results are intended to be descriptive. Evidence that the combination is well tolerated, efficacious and generates activation of immune parameters will provide confidence to move to a more definitive and larger randomized study.

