11.2.8 Immune Endpoints Evaluation

It is expected that pembrolizumab will promote the anti-tumour immune response initiated by the SABR therapy. The working hypothesis is that the induced anti-tumour immune response will be systemic, and this will promote immune surveillance of metastatic lesions. The tumour microenvironment is characterized by an inverse relationship between effector T cells (Teff) and regulatory CD4+ T cells (Treg), tumour associated macrophages (TAM2) and myeloid derived suppressor cells (MDSCs). We expect that SABR+ pembrolizumab (MK-3475) will change this inverse Teff:Suppressor cell balance so that the Teff cells predominate over Tregs and MDSCs. Peripheral blood will be collected before and at intervals during therapy. Alterations in the above immune subsets will be determined by the following (but not limited

to); multi-parameter FACS for T cells (CD3, CD4, CD8, CD45RA, CCR7, CD45Ro), B (CD19), NK (CD3-CD56+CD16+), Treg (CD3,CD4, CD127, FoxP3) and MDSC subsets (CD14+HLADR- and lin-HLADR-CD33+CD15+). We will also examine the immune suppression molecules (TIM3) as well as activation molecules (OX-40) on PB T cell subsets to determine whether these change following treatment with SABR + pembrolizumab.

In the context of renal cancer, therapy-induced tumour-specific T cell responses are difficult to assess as tumour antigens are only partially described. Therefore, we will reveal therapy-induced T cell responses indirectly by examining the TCR repertoire for clonal expansion (next generation sequencing on Illumina).

Lastly, we will examine plasma levels of PD-L1 (sPD-L1) before, during and after therapy to examine whether there is a correlation between patient baseline PD-L1, and whether clinical response correlates with changes in sPD-L1 levels during or after therapy. This will be performed using a commercial ELISA kit assay (see laboratory manual).

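### The plan expects a shift in the balance of effector to suppressor cells but tests each marker's level separately, so that expectation is never tested directly; a pre-specified log-ratio contrast would close the gap cheaply.

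*Combined protocol and SAP*

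**What the plan says.** Section 11.2.8 states the expected immune effect: "We expect that SABR+ pembrolizumab (MK-3475) will change this inverse Teff:Suppressor cell balance so that the Teff cells predominate over Tregs and MDSCs". The background in section 7.10.1 also thinks in relative terms, saying of tumour tissue that "the ratio of CD8+ effector T-cells / FoxP3+ regulatory T-cells seems to correlate with improved prognosis".

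The analysis is in section 11.2.7. The exploratory endpoints, including the peripheral blood markers, go into a linear mixed model: "The linear mixed model will include time as fixed effect (as factor) and patients as random effect". The test is: "Contrasts from the LMM will be used to test whether there is a change in expression levels from baseline to post-treatment sample time points", with cycle 8 and 12 months after SABR named as further contrasts. If the model assumptions fail, "simple descriptive statistics will be provided for each variable at each time point". On scale, the section says only "Variable transformation may be required for some of the collected variables".

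The flow panel in 11.2.8 covers T-cell, Treg and MDSC subsets, and section 7.14 adds the absolute lymphocyte count. Neither section says whether subsets are analysed as absolute counts or as percentages of a parent population.

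Section 11.1 describes the results as descriptive. It also says that evidence that the combination "generates activation of immune parameters will provide confidence to move to a more definitive and larger randomized study".

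**The concern.** The expectation and the test have different null hypotheses. For the balance, the null is that effector and suppressor cells change by the same factor within a patient. For a single-marker contrast, the null is that this one marker does not change. Either can be true while the other is false.

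Two errors follow. If both subsets rise or fall together, the balance is unchanged, yet one marker moves in the hoped-for direction and may be reported as support. If the balance moves modestly while the two subsets vary together, each marker test may be weak although the within-patient ratio is precise.

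At stake is the immune part of the case for a randomised trial, which section 11.1 lists beside tolerability and efficacy. Section 11.2.7 does plan formal contrasts, so significant and non-significant results will be there to be read.

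**Working it through.** **Inputs.** The documents give 30 evaluable patients and the model and contrasts above. They give no power, alpha or variance for the immune contrasts, so there is no plan figure to reproduce. Assumed: log scale; SD of within-patient change (baseline to cycle 8) σ = 0.5 for each subset; correlation ρ between the two changes; n = 18, 24 or 28 patients with both samples; two-sided 5% tests. With two time points and complete data the mixed-model contrast is a paired t test.

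**Formulas.** Let the mean log changes be μ_E (effector) and μ_S (suppressor).
- Single marker: noncentrality μ√n / σ.
- Log ratio: mean μ_E − μ_S, SD σ√(2(1 − ρ)), noncentrality (μ_E − μ_S)√n / [σ√(2(1 − ρ))].

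**1. Balance unchanged, both subsets rise by 0.3.** Teff is significantly up in 67% (n = 18), 80% (n = 24) or 86% (n = 28) of trials. The suppressor is significantly up, which is unfavourable, equally often. What could mislead someone who sees both results is a favourable marker without a significant unfavourable one. At ρ = 0 and n = 18 this is 0.67 × (1 − 0.67) = 0.22. By simulation, as ρ goes from 0 to 0.8:
- n = 18: 22% down to just under 10%
- n = 24: 16% down to about 7%
- n = 28: 12% down to about 5%

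With a common shift of 0.15 the figures lie between about 8% and 22%. A favourable ratio contrast occurs in 2.5% throughout. Teff up together with suppressor down occurs in about 0%. A common fall is the mirror image.

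Sensitivity (n = 30, common 30% change): 3–6% with SD 0.4 and 10–23% with SD 0.6.

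**2. Balance truly shifted, equal split (Teff +0.15, Treg −0.15), n = 24.** Each marker alone has 29% power.

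| ρ | At least one marker favourable | Log ratio |
|---|---|---|
| −0.6 | 42% | 35% |
| −0.3 | 46% | 42% |
| 0 | 50% | 51% |
| 0.3 | 53% | 66% |
| 0.6 | 55% | 88% |
| 0.8 | 57% | 99% |

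For example, at ρ = 0.6 the ratio SD is 0.5 × √0.8 = 0.447 and the noncentrality is 0.3 × √24 / 0.447 = 3.29, which gives 88%.

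**3. Balance truly shifted, all in Teff (+0.3, Treg unchanged), n = 24, ρ = 0.** The Teff contrast has 80% power. The ratio contrast has 51%, because its SD is 0.5 × √2 = 0.707.

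**The case against.** The strongest defence is that the plan matches its stated objective. Exploratory objective 3 in section 6.4 concerns changes over time in blood subsets, and one model per subset answers exactly that. The sentence that 11.2.8 labels its working hypothesis is that the response is systemic. The balance sentence is an expectation that follows a description of the tumour microenvironment, for which a blood ratio is only a proxy. The marker lists are open, so a ratio is not excluded. No decision rule hangs on it, and immune activation in section 11.1 is broader than this balance. All of this stands and lowers the weight of the point. It does not supply a test of the balance, and a ratio chosen after the data are seen would carry less weight than one named now.

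A reader might infer something stronger: that a general rise or fall in lymphocytes would be reported as a favourable shift in 67% to 86% of trials. The documents do not support that, for three reasons. Both markers are tested, and the second moves unfavourably just as often. The scenario needs absolute counts, since percentages of a parent population largely remove a uniform lymphocyte change. MDSCs are myeloid and need not follow lymphocytes at all.

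Nor is the ratio always the more sensitive measure. Section 11.2.8 itself describes an inverse relation between effector and suppressor cells. That does not fix the sign of the correlation between their changes, but negative values cannot be left out, and there the ratio loses power.

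**Conclusion.** The mismatch holds on the text: a balance is expected, levels are tested, and nothing joins the two. Its effect is moderate and conditional. If subsets are analysed as absolute counts and read one at a time, a parallel change leaves an uncontradicted favourable marker in roughly 5% to 22% of trials (SD 0.5, common shifts of 0.15 to 0.3), about 2 to 9 times the 2.5% of a favourable ratio contrast. A real shift is likely to be missed by the single-marker contrasts, yet found by the ratio, mainly when the two changes are positively correlated. At zero or negative correlation the ratio gains no material power and can lose some, and it loses more if only one subset moves. SD, correlation, effect size and numbers with paired samples are all assumptions, so the figures show direction and rough size only.

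This is a worthwhile improvement to an exploratory, descriptive endpoint. It does not touch the primary safety analysis or the secondary endpoints, and it gives no reason to replace the single-marker contrasts.

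**What to change.** In section 11.2.7:

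- Name log(Teff/Treg) and log(Teff/MDSC) as analysis variables, computed per patient and visit from the same sample.
- State the flow-cytometric definition of Teff, which of the two listed MDSC phenotypes enters (or that they are summed), the unit, and a common denominator for both parts of each ratio.
- Fit both in the planned mixed model with the contrasts already listed (cycle 8 and 12 months after SABR).
- Base any statement about the balance in section 11.2.8 on these contrasts, and report the single-marker contrasts alongside, so that a reader sees which component moved.

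The cost is a few lines of SAP text and two derived variables, with no new samples, assays or patients. The downside is two more exploratory variables to test, and a noisier measure when the subsets vary independently or inversely. That is why the component levels should stay in the report.
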